1. Trial period: One to two percutaneous leads are inserted into the epidural space. The distal ends of the leads connect to an external pulse generator (outside the body) that delivers pulses of electricity to dorsal column of spinal cord. The patients live with this trial system for 5-10 days, testing its efficacy in reducing pain intensity and improving function. At the end of trial period, the physician removes the trial leads and discusses the outcome and further steps with the patient. The figure shows a trial system.
2. Implant of permanent device: If the patients experience more than 50% pain relief during trial period, they will undergo a surgery for implanting a permanent device. The permanent device consists of one to two epidural leads and an internal pulse generator. Patient can use a remote control to change between the programs of the device. They can also recharge the batter of the internal pulse generator. The figures show the components of spinal cord stimulator.

Traditional tonic spinal cord stimulation was the only available option for a few decades prior to introduction of newer waveforms in 2015 and 2016. Tonic stimulation delivers one pulse of electricity at frequency of 40-60 hertz. The pulse

width ranges from 200 to 450 microseconds. Patients usually need pulse amplitude of 3.5-8.5 milliamperes. High frequency stimulation increases the frequency to 10,000 hertz and the pulse width is limited to 30 microseconds. The patients usually need amplitudes of 1.5-3.5 milliamperes. High frequency spinal cord stimulation results in more than 50% pain relief in about three quarters of the patients (vs. half of the patients with tonic stimulation).^{4,5} Burst stimulation applies a train of five stacked pulses (without time to discharge between pulses) which is repeated at frequency of 40-60 Hertz. Burst spinal cord stimulation results in more than 50% pain relief in two third of patients.⁶ The figure compares tonic and burst waveforms.

In addition to somatic pain pathway (lateral thalamic pathway), burst spinal cord stimulation also activates medial thalamic pathway as detected by increased EEG activation.¹⁶ This pathway interprets emotional aspects of pain. Thus, clinicians have speculated that this waveform can improve patients' emotional status and mood; however, this is not verified in any clinical studies.

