High Frequency: After randomization, the patient will be scheduled for placement of trial system. We will use Senza® (Nevro Corp., Palo Alto, CA) trial and implant systems to deliver high frequency spinal cord stimulation. A trial system includes two trial leads, an external pulse generator, and a remote control. The permanent implant system includes two leads, an internal pulse generator, a remote control, and a charging device for internal pulse generator. We will use our routine process of trial and implant.

We will position the patients prone on the operating room table, minimizing the lordosis of lumbar spine. We will assist patient comfort and relaxation by nurse-administered moderate sedation titrating doses of midazolam and fentanyl. The patients will be conversing to communicate unusual pain to avoid accidental damage to any neural structures. After

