appropriate skin preparation and draping, fluoroscopy will be used to identify and mark vertebral body levels from T8 to L2. After infiltrating skin and subcutaneous tissue with local anesthetic for analgesia, we will access epidural space at most convenient lumbar space using a 14-gauge Tuohy needle. Epidural access will be confirmed using loss of resistance technique to air with a pulsator syringe. We will then insert an 8-contact, styletted trial lead through the needle. We will advance the lead through posterior epidural space at midline using live fluoroscopy imaging. We will place the tip of the lead at the superior border of T8 vertebral body. We will then access the epidural space and insert a second lead in a similar fashion. The tip of the second lead will be in the middle of T9 vertebral body; the contacts will be staggered with the other lead. We will then check the impedance of the contacts. After confirming appropriate placement, we will remove the needles and lead stylets under live fluoroscopy imaging. We will secure the leads and apply transparent occlusive dressing. We will then transport the patient to post-anesthesia care unit. A representative from the manufacturer will connect the leads to an external pulse generator which will be secured in a small bag around patients' waist. The manufacturer representative will then program the device and will be communicating with the patient daily during the trial period. The trial period will be 5-10 days. We will instruct the patients to maintain the same routine and even try to be more active to test efficacy of the treatment. We will also instruct the patients to keep the dressing, the leads and external pulse generator completely dry. The external pulse generator will deliver the therapy continuously during the trial period. High frequency waveform will be delivered with following parameters: frequency of 10,000 hertz, pulse width of 20 microseconds, and amplitude of 0-15 milliamperes. The patients will return to our clinic at the end of the trial period to remove the trial leads and discuss the treatment outcome. If the patients report more than 50% pain relief and/or improvement in function, they will be scheduled for implant of permanent spinal cord stimulation system at least two weeks after removal of trial leads.

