The trial and implant process will be identical to high frequency with one difference: correct placement of the leads will be confirmed during the trial procedure by inducing paresthesia over the painful area (instead of standard anatomical placement with high frequency). The parameters of the stimulation are as below: each burst includes 5 pulses of electrical stimulation at intra-burst frequency of 500 hertz without time for discharge in between pulses. These bursts will be repeated at inter-burst frequency of 40-60 hertz. The amplitude will range between 0 and 15 milliamperes.

Data Collection: As a part of evaluation for spinal cord stimulation, patients in our clinic complete initial survey on Collaborative Health Outcomes Information Registry (CHOIR). The participants will receive electronic surveys via email at 1, 3, 6, 12, 18, 24 and 36 months after the operation for implant of spinal cord stimulator (or trial in case of failed trial). The participants will receive email reminders after three and five days if the surveys are not completed. If the participants do not complete the surveys within seven days of receipt of the survey link, they will be contacted to be reminded of the survey. These surveys will include average and worst Numerical Rating Scale (NRS) of pain; National Institute of Health (NIH) Patient Reported Outcomes Measurement Information System (PROMIS) measures for function, pain interference, depression and anxiety; patient global impression of change on a 7-point Likert scale; and questions about any adverse events related or unrelated to the therapy. Data about use of other analgesics and medications, and pain interventions

will also be recorded at these intervals from participants' electronic health records and California Prescription Drug Monitoring Program. We will also record participants' baseline characteristics including age, sex, main pain diagnosis, other pain diagnoses, psychological comorbidities, medical comorbidities, medication use, and education level.

Adverse events will be reported to the principal investigator either directly by the participants or through the treating pain physician at Stanford Pain management Center. The principal investigator is responsible for reporting the adverse events and deviations from the protocol appropriately to institutional review board and other authorities.

Mood instability will be monitored as a component of routine clinical care by treating physician.

Outcomes:

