We will use SAS Enterprise Guide (SAS Institute Inc., Cary, NC) for all analyses. Our null hypotheses are similarity of measures. We will perform a two-sided hypothesis testing with accepted type I error of 0.05. We will compare baseline characteristics using t-test for continuous variables and chi-square for categorical variables. We will adjust for the variables that are different between the groups in our final regression model. Our primary analysis will be based on modified intention-to-treat. We will only exclude patients with no follow up data from our final analysis. We will then perform a secondary analysis based on implants only (excluding patients who do not achieve appropriate pain control in trial period).

We will then perform the following subgroup analyses:

1. Patients who have undergone lumbar spine fusion versus patients who have not.
2. Patients with back pain only (based on baseline body map) versus patients with back and leg pain or leg pain only.

3. Patients with PROMIS depression measure of above 90th percentile in baseline evaluation.
4. Patients with PROMIS anxiety measure of above 90th percentile in baseline evaluation.

The rate of CHOIR survey completion is more than 60% in our routine clinical care. We expect a higher rate for our proposed study considering that these surveys are abbreviated, and participants will receive more frequent reminders as well as telephone reminders (currently patients receive only one email reminder to complete the survey). For our primary outcome we will try to minimize missing data by calling the patients who do not complete the surveys up to seven times; we will try to ask and record the pain intensity even if they are not willing to complete surveys. Our analysis model will allow for missing data in longitudinal variables, subject to assumption of missing at random.

Data and Safety Monitoring Plan: We will not perform any interim analyses for benefit, harm or futility. We will establish a data and safety monitoring board consisting of investigators, at least two independent clinicians in our clinic (not part of the study team), and at least one neurosurgeon subspecialized in spine surgery who will monitor the study quarterly for adverse events and patient safety, reporting of adverse events, enrollment pace and study timeline, quality of data, and deviations from the protocol.

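### The secondary implants-only comparison is not protected by randomisation, can be biased if implant rates differ by arm, and has an inconsistently defined patient set

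*Combined protocol and SAP*

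**What the plan says.** The order of events is set out under Approach, Intervention. Randomisation comes first, and in each arm "After randomization, the patient will be scheduled for placement of trial system" with the allocated system. The High Frequency text then gives the study's route to implantation: "If the patients report more than 50% pain relief and/or improvement in function, they will be scheduled for implant". The Burst text makes the process the same except that "correct placement of the leads will be confirmed during the trial procedure by inducing paresthesia over the painful area"; high frequency leads are placed by anatomy. Limitations confirms that neither provider nor participant is blinded.

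On analysis sets, the Analytic Plan says "Our primary analysis will be based on modified intention-to-treat" and "We will only exclude patients with no follow up data from our final analysis". It then adds the secondary analysis: "We will then perform a secondary analysis based on implants only (excluding patients who do not achieve appropriate pain control in trial period").

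Background and Significance, step 2, words the implant criterion differently: "If the patients experience more than 50% pain relief during trial period", with no mention of function. Appropriate pain control is not defined anywhere. No by-arm implant rate is given, the proportion implanted is not among the 11 secondary outcomes, and Limitations does not discuss the implants-only comparison.

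**The concern.** Receiving an implant is a result of the assigned treatment, not a baseline characteristic. It depends on open-label response to the allocated waveform, after a lead-placement step that differs by arm. Comparing implanted patients compares two groups that may have been filtered to different degrees, and randomisation no longer makes them alike.

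Unequal filtering is plausible. Background and Significance quotes more than 50% pain relief in about three quarters of patients with high frequency and two thirds with burst. These are response rates from separate studies, not implant rates.

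The analysis could also carry weight with readers. The sample size is set so that about 80 implanted patients per arm are expected, which is the number the plan requires for 80% power. The result could be read as the effect in treated patients, without the implant rates needed to judge how the groups were selected.

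There is a separate problem of definition. A patient implanted for improved function without adequate pain relief belongs to an implants-only set but is removed by the parenthesis. A patient with good pain control who is not implanted for some other reason is outside the set but is not excluded by the parenthesis. Two analysts could build different datasets.

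**Working it through.** **The plan's own figure.** Inputs from Sample size: SD 2.25, difference 1 NRS unit, two-sided alpha 0.05, power 80%.

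- n per arm = 2 × (1.960 + 0.842)² × 2.25² / 1² = 2 × 7.85 × 5.0625 = 79.5, rounded up to 80. This reproduces.
- With 80% proceeding to implant, 80 / 0.80 = 100 per arm. This reproduces.

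**Selection model (assumed).** Trial response and 12-month improvement are bivariate normal with correlation ρ, and each arm implants the top fraction p of its patients by trial response. Mean standardised response among the implanted then exceeds the arm mean by λ(p) = φ(z)/p, where z cuts off the top fraction p.

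- λ(0.9) = 0.19500 and λ(0.8) = 0.34995, a difference of 0.15495.
- Let D be the 12-month difference before selection, in favour of the arm with more implants. The implants-only difference is D − ρ × 2.25 × 0.15495.
- The amount subtracted is 0.4 × 2.25 × 0.15495 = 0.139 at ρ = 0.4, and 0.6 × 2.25 × 0.15495 = 0.209 at ρ = 0.6.

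The rates of 90% and 80% and the range for ρ are assumptions. The documents give only an overall local rate of more than 80%.

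**Three cases.**

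1. *Equal response, equal implant rates.* The λ terms cancel and the bias is zero.
2. *Common threshold, real difference in response.* Implant rates of 90% and 80% imply a shift in trial response of 1.28155 − 0.84162 = 0.43993 SD. Assume it carries to 12 months through the same ρ. Then D = ρ × 2.25 × 0.43993 = 0.40 (ρ = 0.4) to 0.59 (ρ = 0.6). After selection, 0.396 − 0.139 = 0.26 and 0.5939 − 0.2092 = 0.38. The difference shrinks by 0.15495 / 0.43993 = 35% and keeps its direction.
3. *Implant rates differ but 12-month pain does not (D = 0), or thresholds differ by arm with equal devices.* The implants-only difference is 0.14-0.21 NRS points in favour of the arm with more failed stimulation trials. At ρ = 0.5 it is 0.17 with standard error 0.33 (100 randomised per arm), and a nominal 5% test rejects about 8% of the time.

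**What an implant-rate table can show.** With 100 per arm and 80% implanted in each, the standard error of the difference in proportions is √(2 × 0.8 × 0.2 / 100) = 0.057, so the 95% CI is about ±11 percentage points. Power to detect a true 90% v 80% is about 51%. A non-significant difference in implant rates would therefore not show that selection was equal, which is why the interval should be reported.

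**The definition, side by side.** High Frequency procedure: "If the patients report more than 50% pain relief and/or improvement in function". Background: pain relief only. Analytic Plan: implanted patients, glossed as excluding those without pain control. The gloss fits the Background wording but not the procedure.

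**The case against.** The strongest reply is that the main inference is already protected. This analysis is named secondary, no superiority claim is attached to it, the primary set drops only patients without follow-up data, and Data Collection surveys failed-trial patients on the same schedule. All of that stands, and it limits the point to how one secondary result is defined and read.

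A reader might infer that the analysis generally flatters the device that fails more stimulation trials. The documents do not support that. Apart from lead-placement confirmation, the process is described as the same in both arms, so a common threshold is the natural reading. Under it a real difference is usually attenuated rather than reversed (case 2).

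A reader might also take the 90% and 70% implant rates in Background and Significance as the two arms and calculate a larger bias. Those figures contrast large clinical trials with academic case series. They are overall rates, not rates for high frequency and burst.

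It can also be said that Background describes the therapy in general and that the parenthesis is only a loose gloss. That is fair, but patients implanted for function alone remain ambiguous, and a gloss that contradicts the set it explains should not stay in an analysis plan.

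**Conclusion.** The point holds as a limitation of one secondary analysis. The implants-only comparison selects on a post-randomisation, open-label response to the assigned device, and the plan gives no caveat. Its bias is conditional: zero with equal response and implant rates, usually attenuation under a common threshold, and in favour of the device with more failures only in the circumstances of case 3. The illustrative size in case 3, 0.14-0.21 NRS points, is modest against the 1-point design difference. It rests on assumed by-arm rates, an assumed correlation and a normal model. The inconsistency over who belongs to the set needs no assumption, since it follows from the text. The primary analysis is unaffected.

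**What to change.** - Define the set as all randomised patients who received a permanent implant, whatever the reason, and delete the parenthesis.
- Label the analysis supportive and non-randomised, and state that no superiority claim will be drawn from it.
- Add the proportion of randomised patients implanted, by arm with 95% CI, as a secondary outcome, and report it beside this analysis.
- Adjust for baseline pain, which is already collected, for precision. State that this does not remove the selection.
- Reconcile the implant criterion in Background and Significance, step 2, with the one in the High Frequency procedure, and align the Analytic Plan wording with it. Which criterion applies is for the investigators to settle.

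The cost is a wording change and one extra table, since implant status must be known to run the analysis anyway. The small downside is a more cautious reading of the implants-only result.

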Availability of more diverse and efficacious waveforms and devices has remarkably advanced the field of neuromodulation but has created a dilemma for pain physicians: what is the best waveform and device for **each** patient? Overall superiority of the device as well as its appropriateness in individual patients is very important. We are thus proposing to compare effectiveness of these two new waveforms in patients with chronic back and lower extremity pain. The results of this study will help clinicians make more informed decisions choosing appropriate neuromodulation modality for patients with chronic pain.

(b) Innovation:

Comparing effectiveness of high frequency and burst spinal cord stimulation:

In comparison with conventional medical management (including medications, physical therapy, etc.), spinal cord stimulation results in more superior pain relief in a larger number of patients with chronic refractory pain in trunk and extremities. This treatment can achieve 50% pain relief in about half of the patients.^{2,3} More novel waveforms – high frequency and burst – are even more effective by achieving 50% pain relief in 60-80% of patients.⁴⁻⁶ However, it is unclear if either high frequency or burst spinal cord stimulation works better for all or a subgroup of patients. Our proposed research aims to compare effectiveness of these two novel waveforms in patients with chronic low back and/or leg pain. Moreover, the pragmatic nature of our proposed trial enables us to follow up these patients longer than currently published clinical trials.

Length of Follow-up:

Currently, data is available about safety and efficacy of high frequency and burst spinal cord stimulation for up to 24 months. However, more long-term effectiveness of these treatment modalities has to be established. Our proposed research aims to follow up the patients for 36 months (and possibly longer).

Pragmatic design using point-of-care randomization:

Stanford Pain Management Center enjoys the luxury of an established learning health system – Collaborative Health Outcomes Information Registry (CHOIR) – with capability of point-of-care randomization. This system is already integrated in patient care in our clinic; thus, enrollment, randomization and follow-up data collection will be achieved on the same platform with minimal intrusion in clinical care.

Preliminary Data:

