Sample size: The highest standard deviation of NRS pain scale in our clinic is 2.25 based on prior publications.^{19,21-25} Accepting type I error of 0.05 with 80% power, we will require 80 participants per group to detect one unit between-group difference in change from baseline in NRS pain scale. We are proposing a more conservative (larger) sample size to preserve power considering that some patients do not proceed from trial to implant and do not receive therapy. Currently more than 80% of patients who undergo a trial of spinal cord stimulation proceed to receiving an implant. We will therefore target 100 patients in each arm. Correlation between repeated measure will decrease variance and increase the power of the proposed study.

Timeline: Stanford Pain Management Center performed more than 120 trial of spinal cord stimulation in 2017 and this practice is increasing in our division. We expect a high consent rate considering the nature of our study. We believe we will be able to complete recruitment in two years; thus, last follow up of last recruited patient will be completed by five years.

Data Management: CHOIR will be the main tool for data collection and storage for the study. At completion of the study, the data from CHOIR, participants' electronic health records and California Prescription Drug Monitoring Program will be downloaded for analysis. After initial steps of data preparation, we will de-identify the dataset for further analysis. The principal investigator will save the de-identification code on a secure computer within Stanford University Network only.

Limitations:

1. One of the most important advantages of pragmatic clinical trial with less stringent inclusion/exclusion criteria is to improve the ability to generalize the results to a wider range of patients. However, considering that the current study is a single center study conducted in a tertiary pain management center, our sample might not be representative of chronic pain patients seen by community pain providers.
2. Our aim is to integrate our trial into patient care; thus, we are not blinding the provider and the participants. Method of data collection is similar in both groups and does not involve interaction with investigators. This will minimize, but not eliminate, the bias introduced by proceeding with an open label design.

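### None of the four subgroup analyses has an interaction test, and the depression and anxiety subgroups have no complement, so they cannot show that the waveform effect differs between patients

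*Combined protocol and SAP*

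**What the plan says.** Section (c) Approach, Analytic Plan, lists four subgroup analyses after the primary and implant-only analyses. Previous fusion is written as a contrast: "Patients who have undergone lumbar spine fusion versus patients who have not". Pain location is also written as one group against another. The two mood subgroups are not: "Patients with PROMIS depression measure of above 90th percentile in baseline evaluation" and "Patients with PROMIS anxiety measure of above 90th percentile in baseline evaluation". The plan does not say whether the percentile refers to the trial sample, the registry or a PROMIS norm.

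No outcome, model, interaction term or rule for claiming a difference is given for any subgroup. The only model described has terms for time and treatment. Testing is covered by one general statement, "We will perform a two-sided hypothesis testing with accepted type I error of 0.05", and the subgroups are neither exempted from it nor called exploratory.

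Section (b) Innovation gives the motivation: "it is unclear if either high frequency or burst spinal cord stimulation works better for all or a subgroup of patients". Specific Aim 2 shows how the plan approaches effect modification elsewhere. It stratifies by pain response at one year and states no interaction term.

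**The concern.** Whether one waveform works better in some patients than in others is a question about a difference between treatment effects. An estimate in the top tail alone has nothing to be compared with. Two separate estimates, each with its own p-value, do not test their difference either: the smaller or noisier stratum can miss significance when the effects are identical.

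The risk is a report that one waveform is better in patients with fusion, or in very depressed patients, when the data show no such difference. That could steer the choice of an implanted device. The opposite risk is that a null result in a very small mood subgroup is read as absence of effect.

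**Working it through.** **Inputs.** From Sample size: "The highest standard deviation of NRS pain scale in our clinic is 2.25 based on prior publications"; a 1-point difference; 80% power; "We will therefore target 100 patients in each arm". From the Analytic Plan: two-sided alpha 0.05. The share of patients above the mood cut is not given. I take 10% if the percentile is within the sample and show 20% to 50% for an external norm. The subgroup outcome is not stated either; I use 12-month change in pain, because the documents give an SD for NRS pain but none for PROMIS scores.

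**The plan's own figure.** n per group = 2 × 2.25² × (1.960 + 0.842)² / 1² = 79.5, so 80, as stated ("Accepting type I error of 0.05 with 80% power, we will require 80 participants per group to detect one unit between-group difference"). Dividing by 0.80 gives the target of 100. The sample size reproduces and is not in question.

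**1. Power within a mood subgroup** (two-sample t-test, 1 point, SD 2.25, 100 enrolled per arm):

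| Share above cut | n per arm | Power |
|---|---|---|
| 10% | 10 | 16% |
| 20% | 20 | 28% |
| 30% | 30 | 39% |
| 40% | 40 | 50% |
| 50% | 50 | 60% |

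At 10 per arm the standard error is 2.25 × √(2/10) = 1.01. The 95% CI half-width is 2.1 points, and the difference detectable with 80% power is 2.98 points, about three times the planned effect. With 80 evaluable per arm, 8 remain in the subgroup and power is 13%.

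**2. Separate tests in two strata.** Take two strata of equal size (50 per arm in each; the fusion share is not given) and a true effect of 1 point in both. Power in each is 0.595. The chance that exactly one is significant is 2 × 0.595 × 0.405 = 0.48. With a 30:70 split it is 0.55, and with 20:80 it is 0.63.

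**3. Adding the complement and testing the interaction on the cut.** The standard error is 2.25 × √(2/m + 2/r), with m and r the numbers per arm above and below the cut. For 10 and 90 it is 1.06. Power for a 1-point interaction is 15%, and 2.97 points is detectable with 80% power. This answers the right question, but imprecisely.

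**4. Keeping the score continuous.** The standard error of the treatment-by-score slope, per SD of score, is 2 × 2.25/√200 = 0.318. The detectable slope is 2.80 × 0.318 = 0.89 points per SD. For a normal score, the mean difference between patients above and below the 90th percentile is 1.95 SD. The cut therefore detects 2.97/1.95 = 1.52 points per SD, and the ratio of efficiencies is (1.52/0.89)² = 2.9. If 30% exceed the cut, the ratio is about 1.7. Both ratios assume that the effect changes linearly with the score.

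**5. If the effect changes only at the top.** In a simulation with 200 patients, SD 2.25 and a step of 2.97 points at the 90th percentile, the interaction on the cut had 76% power and the linear term 35%. The advantage in step 4 is then reversed.

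**The case against.** The strongest reply is that the plan states no subgroup method at all, so separate within-stratum p-values are a supposition, and the word versus in the fusion and location items could mean a proper contrast. This stands in part: the 48% describes what happens if the strata are read through separate tests, not a procedure that the plan writes down. It does not rescue the mood subgroups, where no second stratum is named. Specific Aim 2 also shows that stratification without an interaction term is how the plan intends to look for effect modification.

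A second reply is that estimating the effect in very depressed or anxious patients is worthwhile in itself. That stands. High frequency and burst are still compared by randomisation inside the subgroup, and Background and Significance argues that patients with serious psychological conditions need better evidence. A reader might infer that these analyses are invalid or worthless; the documents do not support that.

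A third reply concerns the remedy. A reader might infer that the percentile cuts should be replaced outright by a continuous term because it is 2.9 times as efficient. That figure depends on linear modification. Under a step at the cut the ordering reverses, and the documents do not say which shape is expected. The continuous term is also weak for modest effects: power is about 15% for a slope of 0.3 points per SD and 35% for 0.5.

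Finally, neither Specific Aim and none of the numbered hypotheses concerns these four subgroups. They are secondary, which limits the weight of the point.

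**Conclusion.** The point holds with limits. The listed analyses cannot show that the waveform effect differs between patients, because no interaction is stated for any subgroup and two subgroups have no complement. The randomised estimates inside each subgroup remain valid.

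The size depends on the unstated reference for the percentile. Power of 16% belongs to the within-sample reading; under an external norm exceeded by half the patients it is 60%. For the same reason, a reader might infer that the plan discards most of its data. That can be said only of the two mood analyses, and it fails even there if more than half of patients exceed an external norm. All power figures assume 12-month pain as the outcome and an SD of 2.25. The primary analysis and the sample size are unaffected. The change should be made, but nothing in the main conclusion of the trial depends on it.

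**What to change.** - For all four subgroups, report the treatment-by-subgroup interaction with a 95% CI, from a model fitted in all analysed patients. Base any claim of a subgroup difference on that interaction only, not on within-stratum p-values.
- For depression and anxiety, add a treatment-by-continuous baseline PROMIS score term. Report the treatment difference with a 95% CI at chosen scores, including a high one.
- Keep the high-score subgroup estimate as descriptive, shown with its complement, in case the effect changes only at severe scores. State whose 90th percentile is meant.
- Name the subgroup outcome and label these analyses exploratory.

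This costs SAP wording and a few model terms. Baseline PROMIS scores are already collected in the registry, so no new data are needed. The downside is small: the continuous term assumes roughly linear modification, and with 200 patients it detects a slope of only about 0.89 points per SD, so intervals will be wide for modest interactions.
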